### **7.4.3 Treatment Delays**

Participants who experience a potential DLT must have the study treatment held. Participants who are required to permanently discontinue both study treatments are listed in [Section 8.1](#). In addition, all Grade 2 hepatic, pulmonary, renal, gastrointestinal (GI), and neurological AEs should be evaluated and managed per the toxicity management algorithms ([Appendix 5](#)). Participants not meeting guidelines for permanent discontinuation will be permitted to resume study treatment based on the criteria specified below in [Section 8.1.1](#). Participants eligible to resume study treatment will resume study treatment at the visit following their last received dose.

If the reason for a dosing delay is not due to a potential DLT, then the DLT evaluation period may be extended to include at least 28 days after the start of the sequential doses in Part 1 or at least 14 days after the start of Cycle 2 Day 1 sequential doses in Part 2 to allow for adequate time to observe any potential DLTs following these sequential administrations.

Extensions to the period of dose delays may be granted for individual participants on a case-by-case basis after specific consultation and agreement between the investigator and BMS Medical Monitor (or designee) in settings where benefit/risk may justify continued study treatment (eg, participant deriving clinical benefit who requires prolonged steroid taper for the management of non-DLT drug-related AEs or experiences delays for the management of a nondrug-related AE).

The tumor assessments (ie, CT/MRI, positron emission tomography [PET], etc) will continue relative to the participant's first dose as outlined in [Section 2](#) (Schedule of Activities) regardless of any treatment delay incurred.

### **7.4.4 Exceptions to Permanent Discontinuation Criteria**

Detailed exceptions to permanent discontinuation are listed in [Section 8.1](#).

Any drug-related AE occurring at any time that meets DLT criteria as outlined in [Section 7.4.1](#) will require permanent discontinuation except in cases of non-life-threatening AEs that meet DLT criteria and that have been resolved to Grade 1 or baseline. In these specific cases consideration to resume treatment will be made on a case-by-case basis in a discussion between the investigator and BMS Medical Monitor (or designee), taking into account the overall benefit/risk ratio for the individual participant and considering the following factors:

- A 2-week washout period is required after completing the immune suppressive treatment used to manage the AE (eg, steroids). The AE should not recur/worsen during the washout period.
- Evidence for clinical or radiographic benefit must be present, which can include improvement of physical symptoms (eg, ECOG status, shortness of breath), symptomatic improvement in combination with assessment of SD, or radiographic response.

In the event of recurrence of the AE that met the DLT criteria, study therapy will be permanently discontinued for the participant.

Additionally, consideration to permanently discontinue study therapy for participants with any severe Grade 3 drug-related AE that recurs will be made on a case-by-case basis in a discussion between the investigator and BMS Medical Monitor (or designee).

All participants who discontinue treatment should comply with protocol-specified follow-up procedures as outlined in [Sections 2](#) (Schedule of Activities) and [5.1.5](#). The only exception to this requirement is when a participant withdraws consent for all study procedures including post-treatment study follow-up or loses the ability to consent freely (eg, imprisonment or involuntarily incarceration for the treatment of either a psychiatric or physical illness).

If study treatment is discontinued prior to the participant's completion of the study, the reason for the discontinuation must be documented in the participant's medical records and entered on the appropriate Case Report Form (CRF) page.

#### **7.4.5 Management of Drug-related Infusion Reactions**

BMS-986277 has the potential to induce hypersensitivity reactions following administration. There is potential risk of cytokine release exhibited with enadenotucirev coupled with potential immune activation from transgenes. These events will be mitigated by an up to 12 hour post infusion observation, laboratory measurements for cytokine release monitoring, staggered dosing of initial participants in each cohort of monotherapy treatment (Part 1) and combination treatment (Part 2) to have no more than 1 patient at a time dosed, and a starting dose selected that is 100 $\times$  below the enadenotucirev RP2D. Refer to [Appendix 10](#) for the treatment algorithm for BMS-986277-associated infusion reactions.

Since nivolumab contains only human immunoglobulin protein sequences, it is unlikely to be immunogenic and induce infusion or hypersensitivity reactions. However, if such a reaction were to occur, it might manifest with fever, chills, rigors, headache, rash, pruritus, arthralgia, hypotension, hypertension, bronchospasm, or other allergic-like reactions. All Grade 3 or 4 infusion reactions should be reported within 24 hours to the study Medical Monitor (or designee) and reported as an SAE if it meets the criteria. Infusion reactions should be graded according to NCI CTCAE (Version 4.03) guidelines.

Treatment recommendations for nivolumab-associated infusion reactions are provided below and may be modified based on local treatment standards and guidelines, as appropriate:

**For Grade 1 symptoms** (mild reaction; infusion interruption not indicated; intervention not indicated):

- Remain at bedside and monitor participant until recovery from symptoms. The following prophylactic premedications are recommended for future infusions: diphenhydramine 50 mg IV (or equivalent) and/or acetaminophen/paracetamol 325 to 1000 mg at least 30 minutes before additional nivolumab administrations.

[figure not shown]
**For Grade 2 symptoms:** (moderate reaction required therapy or infusion interruption but responds promptly to symptomatic treatment (eg, antihistamines, non-steroidal anti-inflammatory drugs, narcotics, corticosteroids, bronchodilators, IV fluids); prophylactic medications indicated for  $\leq 24$  hours):

- Stop the study drug infusion, begin an IV infusion of normal saline, and treat the participant with diphenhydramine 50 mg IV (or equivalent) and/or acetaminophen/paracetamol 325 to 1000 mg; remain at bedside and monitor participant until resolution of symptoms. Corticosteroid and/or bronchodilator therapy may also be administered as appropriate. If the infusion is interrupted, then restart the infusion at 50% of the original infusion rate when symptoms resolve; if no further complications ensue after 30 minutes, the rate may be increased to 100% of the original infusion rate. Monitor participant closely. If symptoms recur, then no further study medication will be administered at that visit.
- For future infusions, the following prophylactic premedications are recommended: diphenhydramine 50 mg IV (or equivalent) and/or acetaminophen/paracetamol 325 to 1000 mg should be administered at least 30 minutes before treatment infusions. If necessary, corticosteroids (up to 25 mg of hydrocortisone or equivalent) may be used.

**For Grade 3 or 4 symptoms:** (severe reaction, Grade 3: prolonged [ie, not rapidly responsive to symptomatic medication and/or brief interruption of infusion]; recurrence of symptoms following initial improvement; hospitalization indicated for other clinical sequelae (eg, renal impairment, pulmonary infiltrates). Grade 4: Life threatening; pressor or ventilatory support indicated):

- Immediately discontinue infusion of study drug. Begin an IV infusion of normal saline and treat the participant as follows: Recommend bronchodilators, epinephrine 0.2 to 1 mg of a 1:1000 solution for subcutaneous administration or 0.1 to 0.25 mg of a 1:10,000 solution injected slowly for IV administration, and/or diphenhydramine 50 mg IV (or equivalent) with methylprednisolone 100 mg IV (or equivalent), as needed. Participant should be monitored until the Investigator is comfortable that the symptoms will not recur. Study drug will be permanently discontinued. Investigators should follow their institutional guidelines for the treatment of anaphylaxis. Remain at bedside and monitor participant until recovery of the symptoms.

In case of late-occurring hypersensitivity symptoms (eg, appearance of a localized or generalized pruritus within 1 week after treatment), symptomatic treatment may be given (eg, oral antihistamine or corticosteroids).

### **7.5 Preparation/Handling/Storage/Accountability**

The investigational product should be stored in a secure area according to local regulations. It is the responsibility of the investigator to ensure that investigational product is only dispensed to study Participants. The investigational product must be dispensed only from official study sites by authorized personnel according to local regulations.

The product storage manager should ensure that the study treatment is stored in accordance with the environmental conditions (temperature, light, and humidity) as determined by BMS. If concerns regarding the quality or appearance of the study treatment arise, the study treatment should not be dispensed and contact BMS immediately.

Study treatment not supplied by BMS will be stored in accordance with the package insert.

Investigational product documentation (whether supplied by BMS or not) must be maintained that includes all processes required to ensure drug is accurately administered. This includes documentation of drug storage, administration and, as applicable, storage temperatures, reconstitution, and use of required processes (eg, required diluents, administration sets).

Further guidance and information for final disposition of unused study treatment are provided in [Appendix 2](#) and the Pharmacy Manual.

#### **7.5.1 Retained Samples for Bioavailability/Bioequivalence**

Not applicable.

### **7.6 Treatment Compliance**

Not applicable.

[REDACTED]

## **7.8 Treatment After the End of the Study**

At the end of the study, BMS will not continue to provide BMS supplied study treatment to participants/investigators unless BMS chooses to extend the study. The investigator should ensure that the participant receives appropriate standard of care to treat the condition under study.

## **8 DISCONTINUATION CRITERIA**

### **8.1 Discontinuation from Study Treatment**

Participants MUST discontinue investigational product (and non-investigational product at the discretion of the investigator) for any of the following reasons:

- Participant's request to stop study treatment. Participants who request to discontinue study treatment will remain in the study and must continue to be followed for protocol specified follow-up procedures. The only exception to this is when a participant specifically withdraws consent for any further contact with him/her or persons previously authorized by participant to provide this information
- Any clinical AE, laboratory abnormality or intercurrent illness which, in the opinion of the investigator, indicates that continued participation in the study is not in the best interest of the participant
- Termination of the study by Bristol-Myers Squibb (BMS)
- Loss of ability to freely provide consent through imprisonment or involuntarily incarceration for treatment of either a psychiatric or physical (eg, infectious disease) illness. (Note: Under specific circumstances, a participant who has been imprisoned may be permitted to continue as a participant. Strict conditions apply and BMS approval is required.)
- Pregnancy

- Documented and confirmed disease progression as defined by RECIST v1.1 or PCWG3 (Appendix 7 and 8, respectively) unless participants meet criteria for treatment beyond progression (Section 8.1.2)
  - Clinical deterioration while receiving active study treatment that, in the opinion of the investigator, indicates that continued participation in the study is not in the best interest of the participant
  - Discretion of the investigator
  - Inability to comply with the protocol requirements
  - Individual participants with confirmed CR will be given the option to discontinue study treatment on a case-by-case basis after specific consultation and agreement between the investigator and BMS Medical Monitor (or designee) in settings where benefit/risk justifies discontinuation of study treatment
  - Any drug-related AE occurring at any time that meets DLT criteria as outlined in Section 7.4.1 will require permanent discontinuation except in cases of non-life-threatening AEs that meet DLT criteria and that have been resolved to Grade 1 or baseline. See Section 8.1.1 for considerations regarding resuming treatment.
  - Any Grade  $\geq 2$  study treatment-related pneumonitis or interstitial lung disease that does not resolve following dose delay and systemic steroids
  - Any Grade 3 non-skin, study treatment-related AE lasting  $> 7$  days, or recurs, with the following exceptions for uveitis, pneumonitis, bronchospasm, diarrhea, colitis, neurologic toxicity, myocarditis, hypersensitivity reactions, infusion reactions not returning to baseline in  $\leq 1$  hour, endocrinopathies and laboratory abnormalities:
    - Grade 3 drug-related uveitis, pneumonitis, bronchospasm, neurologic toxicity, myocarditis, hypersensitivity reaction of any duration, or infusion reaction not returning to baseline in  $\leq 1$  hour requires discontinuation
    - Grade 3 study treatment-related endocrinopathies adequately controlled with only physiologic hormone replacement do not require discontinuation. Adrenal insufficiency requires discontinuation regardless of control with hormone replacement.
    - Grade 3 drug-related laboratory abnormalities do not require treatment discontinuation except:
      - ◆ Grade 3 drug-related thrombocytopenia  $> 7$  days or associated with bleeding requires discontinuation
      - ◆ Grade  $\geq 3$  drug-related AST, ALT or Total Bilirubin requires discontinuation\*
      - ◆ Concurrent AST or ALT  $> 3 \times$  ULN and total bilirubin  $> 2 \times$  ULN
- \* In most cases of Grade 3 AST or ALT elevation, study treatment will be permanently discontinued. If the investigator determines a possible favorable benefit/risk ratio that warrants continuation of study treatment, a discussion between the investigator and the BMS Medical Monitor/designee must occur.
- Any Grade 4 drug-related AE or laboratory abnormality (including but not limited to creatinine, AST, ALT, or Total Bilirubin), except for the following events which do not require discontinuation:
    - Grade 4 neutropenia  $\leq 5$  days

- Grade 4 lymphopenia or leukopenia or asymptomatic amylase or lipase
- Isolated Grade 4 electrolyte imbalances/abnormalities that are not associated with clinical sequelae and are corrected with supplementation/appropriate management within 72 hours of their onset
- Grade 4 drug-related endocrinopathy AEs, such as, hyper- or hypothyroidism, or glucose intolerance, which resolve or are adequately controlled with physiologic hormone replacement (corticosteroids, thyroid hormones) or glucose-controlling agents, respectively, may not require discontinuation after discussion with and approval from the BMS Medical Monitor (or designee). Grade 4 adrenal insufficiency must discontinue.
- Any event that leads to delay in dosing lasting > 6 weeks from the previous dose requires discontinuation, with the following exceptions:
  - Dosing delays to allow for prolonged steroid tapers to manage drug-related AEs are allowed.
  - Dosing delays lasting > 6 weeks from the previous dose that occur for non-drug-related reasons may be allowed if approved by the BMS Medical Monitor (or designee).

Prior to re-initiating treatment in a participant with a dosing delay lasting > 6 weeks, the BMS Medical Monitor (or designee) must be consulted.

Tumor assessments should continue as per protocol even if dosing is delayed. Periodic study visits to assess safety and laboratory studies should also continue every 6 weeks or more frequently if clinically indicated during such dosing delays.

Refer to the Schedule of Activities for data to be collected at the time of treatment discontinuation and follow-up and for any further evaluations that can be completed

In the case of pregnancy, the investigator must immediately, within 24 hours of awareness of the pregnancy, notify the BMS Medical Monitor/designee of this event. In most cases, the study treatment will be permanently discontinued in an appropriate manner (eg, dose tapering if necessary for participant safety). Refer to [Section 9.2.5](#) Pregnancy.

All participants who discontinue study treatment should comply with protocol specified follow-up procedures as outlined in [Section 2](#). The only exception to this requirement is when a participant withdraws consent for all study procedures including post-treatment study follow-up or loses the ability to consent freely (ie, is imprisoned or involuntarily incarcerated for the treatment of either a psychiatric or physical illness).

If study treatment is discontinued prior to the participant's completion of the study, the reason for the discontinuation must be documented in the participant's medical records and entered on the appropriate case report form (CRF) page.

The assessment for discontinuation of nivolumab should be made separately from the assessment made for discontinuation of BMS-986277. Although there is overlap among the discontinuation criteria, if discontinuation criteria are met for BMS-986277 but not for nivolumab, treatment with nivolumab may continue if BMS-986277 is discontinued.

If a participant in any of the nivolumab/BMS-986277 combination arms meets criteria for discontinuation and investigator is unable to determine whether the event is related to both or one study drug, the participant should discontinue both nivolumab and BMS-986277 and be taken off the treatment phase of the study.

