### 2) Non-hepatic Non-hematological DLT

Any of the following events will be considered a non-hepatic non-hematological DLT:

- Any Grade 2 drug-related uveitis or eye pain or blurred vision that does not respond to topical therapy and does not improve to Grade 1 severity  $\leq 2$  weeks *or* requires systemic treatment.
- Grade 3 drug-related uveitis, pneumonitis, bronchospasm, neurologic toxicity, hypersensitivity reaction, or myocarditis, of any duration or infusion reaction not returning to baseline in  $< 1$  hour, will require discontinuation.

- Any Grade 3 or greater nondermatologic, nonhepatic nonhematological study treatment-related toxicity will be considered a DLT, with the following specific exceptions:
  - ◆ Grade 3 or Grade 4 electrolyte abnormalities that are not complicated by associated clinical adverse experiences, last less than 72 hours, and either resolve spontaneously or respond to conventional medical intervention
  - ◆ Grade 3 nausea, vomiting, or diarrhea that lasts less than 72 hours, and either resolves spontaneously or responds to conventional medical intervention
  - ◆ Isolated Grade 3 elevation of amylase or lipase not associated with clinical or radiographic evidence of pancreatitis
  - ◆ Isolated Grade 3 fever not associated with hemodynamic compromise (eg, hypotension, clinical or laboratory evidence of impaired end-organ perfusion or with other symptoms of infusion-related reactions that returns to  $\leq$  Grade 1 with standard treatment in  $\leq$  1 hour)
  - ◆ Grade 3 endocrinopathy that is well controlled by hormone replacement
  - ◆ Grade 3 tumor flare (defined as pain, irritation, or rash that localizes to sites of known or suspected tumor)
  - ◆ Grade 3 fatigue for  $\leq$  7 days
  - ◆ Grade 3 infusion reaction that returns to Grade 1 in  $\leq$  1 hour

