### **8.1.1 Criteria to Resume Treatment**

Participants will be permitted to resume study treatment at the same dose level(s) following resolution of the AE to  $\leq$  Grade 1 or to baseline with the exception of participants who meet criteria for permanent discontinuation of study treatment (see [Section 8.1](#)):

- For participants receiving two cycles of combination treatment, the first dose of BMS-986277 in Cycle 2 may be delayed by up to 7 days (up to study Day 36) in the case of persistence of AEs from the preceding cycle as listed above. After this time, nivolumab monotherapy may be continued.
- Nivolumab dosing may be delayed by up to 6 weeks; the participant should restart treatment on the next regularly scheduled nivolumab dosing visit. Doses are not to be replaced only delayed. If nivolumab treatment is delayed  $> 6$  weeks the participant must permanently discontinue study treatment except as specified in Section 8.1.

Tumor assessments for all participants should continue according to the schedule of assessments ([Section 2](#)) **even if dosing is delayed**.

Participants may resume treatment with study treatment when the drug-related AE(s) resolve to Grade  $\leq 1$  or baseline value, with the following exceptions:

- Participants may resume treatment in the presence of Grade 2 fatigue.
- Participants who have not experienced a Grade 3 drug-related skin AE may resume treatment in the presence of Grade 2 skin toxicity.
- For participants with Grade 2 AST, ALT and/or Total Bilirubin Abnormalities, dosing may resume when laboratory values return to baseline and management with corticosteroids, if needed, is complete.
- Drug-related pulmonary toxicity, diarrhea or colitis must have resolved to baseline before treatment is resumed. Participants with persistent Grade 1 pneumonitis after completion of a steroid taper over at least 1 month may be eligible for retreatment if discussed with and approved by BMS Medical Monitor (or designee).

Participants with drug-related endocrinopathies adequately controlled with only physiologic hormone replacement may resume treatment after consultation with the BMS Medical Monitor (or designee). Adrenal insufficiency (Grade 4) requires discontinuation regardless of control with hormone replacement.

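### Protocol sections are inconsistent on whether Grade 3 adrenal insufficiency, or a Grade 3 nivolumab infusion reaction that resolves within one hour, ends treatment

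*Protocol*

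**What the plan says.** **Adrenal insufficiency**

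- Protocol Section 8.1, inside the bullet on Grade 3 endocrinopathies: "Adrenal insufficiency requires discontinuation regardless of control with hormone replacement". A later bullet on Grade 4 events adds: "Grade 4 adrenal insufficiency must discontinue".
- Protocol Section 8.1.1: "Participants with drug-related endocrinopathies adequately controlled with only physiologic hormone replacement may resume treatment", after consultation with the Medical Monitor. The next sentence reads: "Adrenal insufficiency (Grade 4) requires discontinuation regardless of control with hormone replacement".
- Section 8.1.1 also opens by allowing resumption "with the exception of participants who meet criteria for permanent discontinuation of study treatment", with a pointer to Section 8.1.

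**Nivolumab infusion reaction**

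- Protocol Section 7.4.5, for Grade 3 or 4 symptoms: "Study drug will be permanently discontinued". No time limit is attached. The list is introduced as treatment recommendations that may be adapted to local standards.
- Protocol Section 8.1 requires discontinuation for a Grade 3 infusion reaction when it has not returned to baseline in one hour or less.
- Protocol Section 7.4.1 uses two other criteria. One bullet covers a Grade 3 infusion reaction not back at baseline in less than one hour. A listed exception to the general Grade 3 DLT rule covers one back at Grade 1 in one hour or less.

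**Diarrhea and colitis (minor)**

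- Protocol Section 8.1 stops treatment for Grade 3 non-skin related events that last more than 7 days or recur, "with the following exceptions for uveitis, pneumonitis, bronchospasm, diarrhea, colitis, neurologic toxicity, myocarditis, hypersensitivity reactions" and others. The sub-bullets that follow do not mention diarrhea or colitis.

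**The concern.** A site with a participant who has Grade 3 adrenal insufficiency controlled on hormone replacement, or a Grade 3 nivolumab reaction that clears quickly, can reach a different decision depending on which section it opens. Protocol Section 9 allows no waivers, so following one section may be a deviation from another.

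The statistical consequence runs through the primary endpoint. AEs leading to discontinuation is a primary safety endpoint in both documents, and SAP Sections 5.1.1 and 8.6.4 derive it from the action recorded for each AE. If two sites read the rules differently, the tabulated rate reflects that difference as well as tolerability.

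**Working it through.** The documents give no figure to reproduce here. The check sets the sections side by side for defined cases.

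**Case A: Grade 3 adrenal insufficiency, controlled on physiologic hormone replacement**

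1. Section 8.1 stops treatment. Its sentence cannot be read as Grade 4 only, because it sits in the Grade 3 bullet and Grade 4 has its own sentence further down.
2. The endocrinopathy paragraph of Section 8.1.1 permits resumption after consultation and limits the adrenal stop to Grade 4. By implication, Grade 3 may resume.
3. The opening of Section 8.1.1 excludes anyone who meets the Section 8.1 criteria, which leads back to a stop.
4. If step 3 governs, the Grade 4 limit in Section 8.1.1 does no work and misleads. If it does not govern, Sections 8.1 and 8.1.1 disagree.

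**Cases B to D: Grade 3 nivolumab infusion reaction**

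| Course | 7.4.5 | 8.1 infusion-reaction rule | 7.4.1 bullet | 7.4.1 exception |
|---|---|---|---|---|
| B. Baseline well inside one hour | Stop | Stop not required | Not met | Not a DLT |
| C. Grade 1, but not baseline, by one hour | Stop | Stop | DLT, stop | Not a DLT |
| D. Baseline at exactly one hour | Stop | Stop not required | DLT, stop | Not a DLT |

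Sections 7.4.5 and 8.1 differ in B and D. The two parts of Section 7.4.1 differ in C and D, unless the exception is read as attaching only to the general Grade 3 rule and not to the bullet before it. The text does not say.

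**Diarrhea and colitis: which other rules apply**

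- Section 7.4.1: related Grade 3 toxicity of this class is a DLT. Diarrhea is excepted only if it lasts under 72 hours and resolves or responds to treatment; colitis has no exception. Diarrhea lasting more than 7 days exceeds 7 × 24 = 168 hours, so it falls outside the exception.
- Section 8.1: an AE meeting DLT criteria at any time requires a permanent stop unless it is non-life-threatening and has resolved to Grade 1 or baseline.
- Section 7.4.4: recurrence of such an AE is a permanent stop. Other recurrent severe Grade 3 events are decided case by case.
- Section 7.4.2 delays dosing at Grade 2 or above, and Section 8.1.1 requires resolution to baseline before resumption.

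Recurrent Grade 3 diarrhea with each episode under 72 hours and responding is left to the case-by-case provision.

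**Size on the endpoint**

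Protocol Section 5.2 starts dose levels with 3 to 6 participants. One participant whose status turns on the reading moves the discontinuation rate by 1/6 = 16.7 points at n = 6, or 1/3 = 33.3 points at n = 3. For that participant, up to 26 − 1 = 25 nivolumab doses depend on the reading, if the event follows the first dose.

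**The case against.** The strongest reply is that each conflict is narrower than it looks.

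- **Adrenal insufficiency.** Section 8.1.1 defers to Section 8.1, no sentence says that a Grade 3 case may resume, and the Medical Monitor must be consulted first. A reader might infer opposite instructions; with the deference clause in place, the documents do not go that far. The mismatch in grade still stands. Deference ranks the sections without explaining why one restates the rule more narrowly, and consultation gives the Medical Monitor no settled text to apply.
- **Infusion reaction.** Section 8.1 lists reasons that compel a stop and never says that a quickly resolving reaction may continue, so Section 7.4.5 could be an added, stricter instruction. Section 7.4.5 also describes Grade 3 partly as prolonged, which reduces the overlap, and Grade 3 or 4 reactions go to the Medical Monitor within 24 hours. Against this, Sections 7.4.1 and 8.1 both contemplate a Grade 3 reaction that clears within an hour. If Section 7.4.5 always applied, the time limit in Section 8.1 would have no effect for nivolumab. Calling the list recommendations open to local change makes a permanent stop more variable, not less.
- **Diarrhea and colitis.** A reader might infer that no rule governs them. That is not supported: the DLT stop, recurrence, delay and resume rules all reach them. Section 7.4.3 also points to toxicity algorithms in Appendix 5, which are not in the public text. Only the missing sub-bullet or cross-reference remains.

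**Conclusion.** The point holds for two events. Protocol Sections 8.1 and 8.1.1 give different grades for the adrenal insufficiency stop. Sections 7.4.1, 7.4.5 and 8.1 do not share one outcome or one recovery criterion for a Grade 3 nivolumab infusion reaction. The diarrhea and colitis list is a minor drafting gap.

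The size is conditional. One affected participant is worth 17 to 33 points in a dose level of 6 or 3, but the documents give no frequency for these events, so no expected bias can be stated. The infusion-reaction conflict cannot arise in Part 1, which has no nivolumab. Discontinuation is also assessed separately for each drug.

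Three further inferences are not supported:

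- The DLT list exempts "Grade 3 endocrinopathy that is well controlled by hormone replacement", and a reader might see a contradiction with a stop under Section 8.1. There is none. DLTs are defined to guide escalation, and nothing says that every stop must be a DLT.
- A reader might infer that a participant stopped for such an event is counted in escalation as free of DLT. Sections 7.2 and 7.4.1 allow replacement of participants who are not DLT-evaluable or who withdraw for other reasons, and Section 10.1.1.1 brings all available data into the clinical assessment.
- A mismatch in the recorded discontinuation reasons cannot be claimed, because the case report form is not among the documents.

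**What to change.** Reconcile Protocol Sections 7.4.1, 7.4.5, 8.1 and 8.1.1 so that:

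1. Grade 3 adrenal insufficiency has one stated outcome, with the same grade wording in Sections 8.1 and 8.1.1.
2. A Grade 3 nivolumab infusion reaction has one stated outcome and one recovery criterion (baseline or Grade 1, and a single form of the one-hour limit). Section 7.4.5 should say whether its stop instruction is binding or a recommendation.
3. Section 8.1 states, or cross-refers to, the rule for Grade 3 diarrhea and colitis.

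Which rule applies is for the clinical team; none is proposed here. The cost is wording in the next protocol revision, with no added participants and no change to the analysis methods.
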